- Review of the child's asthma action plan. By this point, the CHW will have retrieved the asthma action plan for the child's PCP to review with the family.
- Review of child's medications and importance of using them as prescribed.
 - Barriers to using medications for family will be reviewed. CHW and caregiver will problem solve ways to increase adherence.
 - Issues with insurance coverage, prescription payments, and refills are also discussed, as well as strategies for minimizing these issues.
- Healthy Homes role: Review changes that family has made (if any) based on first assessment. Session content includes:
 - Praise for successful changes. Review how family was able to make these important changes.
 - Problem solve issues that have prevented any changes that family wanted to make.
 - Review new priority areas and how family can make these changes.
 - Assess whether follow up with landlord or referral to Medical-Legal Partnership is needed.
 - Address any additional needs that family may have related to home environmental remediation.
 - Set goals for any behavioral modifications/changes in the home that are needed between now and the next visit.
- CHWs and Healthy Homes assessors complete a session checklist of material covered; caregivers also independently complete a checklist.
- Schedule the next session, Session 3, before leaving the family's home. Schedule a follow up phone call for each month before the next session. Remind the family that the CHW will be calling then. Make sure the family has all contact information for RVA Breathes.
- Answer any questions the family has and thank them for their time.

Changes due to COVID-19:

- Session occurs over the phone or via video (see Section E3)
- Questions added to packet:
 - "How has the COVID-19 pandemic impacted you and your family?"
 - "What did you think of the phone/video session today instead of an in-person visit?"
- Intervention materials dropped off using contactless procedures (see Section E3)

E8 Session 3, Month 7

During Month 7 of study participation, families in the two active intervention arms will complete the third of 4 sessions. For children in the CHW + Healthy Homes + school intervention arm and children in the CHW + Healthy Homes intervention arm, this will be the third home visit that includes both family-based asthma education and a home assessment by Healthy Homes. Home visits will last 2-2.5 hours, and include both the CHW and a representative from Healthy Homes. The intervention component related to home environmental remediation will reduce in intensity with each session.

CHWs in consultation with the care management committee, will continue to update providers on the family's participation in the intervention. Data from family interactions with the PCP will be communicated back to CHWs.

For children in the CHW + Healthy Homes + school intervention arm, CHWs will continue to communicate with the schools to ensure that children have the necessary forms and medication in place. School nurses will

continue to follow the standardized protocol in their interactions with the student; interactions will be documented and relayed to CHWs.

For children in the E-SOC group the project coordinator will mail the third set of publicly available information on asthma.

Intervention Session 3:

- CHW and Healthy Homes worker summarize the information that was covered in the first and second visits.
- The caregiver and child are asked for an update on any changes in medication, and any asthma-related sick visits, scheduled visits, hospitalizations, ED visits, or absenteeism.
- CHW role: Lesson plans focus on communication with providers, school and family issues related to asthma. Content includes:
 - Review child and caregiver's experiences and relationship with asthma care provider.
 - Discuss the role of school nurses and how families can communicate with schools about their children's asthma.
 - CHW reviews how asthma interferes with child's functioning throughout the school day, including during recess, gym, or walking through the halls. Discussion also focuses on how child handles such occurrences and how having asthma symptoms during the school day can make it harder to pay attention.
 - Strategies to improve preventive actions, such as using daily controller, will be reviewed.
 - Management of asthma within the family is reviewed, including which family members are responsible for which aspects of daily asthma care.
 - Decisions regarding when child is taken to the emergency department are reviewed.
 - Review of caregiver functioning and stress. Focuses on importance of parent caring for him or herself in order to provide child with best care possible.
- Healthy Homes role: Review changes that family has made (if any) based on first and second visits. Session content includes:
 - Praise for successful changes. Review how family was able to make these important changes.
 - Problem solve issues that have prevented any changes that family wanted to make.
 - Review new priority areas and how family can make these changes.
 - Assess whether follow up with landlord or referral to Medical-Legal Partnership is needed.
 - Address any additional needs that family may have related to home environmental remediation.
 - Set goals for any behavioral modifications/changes in the home that are needed between now and the next visit.
- CHWs and Healthy Homes assessors complete a session checklist of material covered; caregivers also independently complete a checklist.
- Schedule the next session, Session 4, before leaving the family's home. Schedule a follow up phone call for each month before the next session. Remind the family that the CHW will be calling then. Make sure the family has all contact information for RVA Breathes.
- Answer any questions the family has and thank them for their time.

Changes due to COVID-19:

- Session occurs over the phone or via video (see Section E3)
- Questions added to packet:
 - "How has the COVID-19 pandemic impacted you and your family?"
 - "What did you think of the phone/video session today instead of an in-person visit?"
- Intervention materials dropped off using contactless procedures (see Section E3)

E9 Session 4, Month 9

During Month 9 of study participation, families in the two active intervention arms will complete the final intervention sessions. For children in the CHW + Healthy Homes + school intervention arm and children in the

CHW + Healthy Homes intervention arm, this will be the fourth home visit that includes both family-based asthma education and a home assessment by Healthy Homes. Home visits will last 2-2.5 hours, and include both the CHW and a representative from Healthy Homes. This session will focus on reinforcing previously learned material and setting goals for sustaining change and preventive behaviors.

CHWs, in consultation with the care management committee, will continue to update providers on the family's participation in the intervention. Data from family interactions with the PCP will be communicated back to CHWs.

For children in the CHW + Healthy Homes + school intervention arm, CHWs will continue to communicate with the schools to ensure that children have the necessary forms and medication in place. School nurses will continue to follow the standardized protocol in their interactions with the student; interactions will be documented and relayed to CHWs.

For children in the E-SOC group the project coordinator will mail the fourth set of publicly available information on asthma.

Intervention Session 4:

- The caregiver and child are asked for an update on any changes in medication, and any asthma-related sick visits, scheduled visits, hospitalizations, ED visits, or absenteeism.
- CHW and Healthy Homes worker summarize the information that has been covered in the last three sessions.
- Time is spent reviewing any lessons that have been challenging for the family to master.
- CHW role: Lesson plans focus on empowering families. Content includes:
 - Discuss issues in the school or community that impact childhood asthma.
 - Outline strategies for family to focus efforts on appropriate self-management behaviors, including using medications correctly, recognizing symptoms, communicating with providers, and enhancing preventive care.
 - Summarize family's strengths and how they can work together as a team in managing child's asthma.
 - Encourage continued communication between family and primary care providers.
 - Address any other issues that the family raises.
- Healthy Homes role: Review any changes that family has made and/or maintained since the last sessions. Session content includes:
 - Praise for successful changes. Review how family was able to make these important changes.
 - Problem solve issues that have prevented any changes that family wanted to make.
 - Review new priority areas and how family can make these changes. Focus on empowering the family to continue to implement changes in their home.
 - Assess whether follow up with landlord or referral to Medical-Legal Partnership is needed.
 - Address any additional needs that family may have related to home environmental remediation.
 - Set clear plans for maintaining these changes.
- CHWs and Healthy Homes assessors complete a session checklist of material covered; caregivers also independently complete a checklist.
- Wrap up with a review of everything that was accomplished in the year long program. Make sure that the parent and child will keep their RVA Breathes binders in a safe place for easy reference.
- Provide a certificate of completion to both the parent and child.
- Schedule the post-intervention session before leaving the family's home.
- Answer any questions the family has and thank them for their time. Stress the importance of continued participation for the next 9 months, even though they have completed the four intervention sessions.

Changes due to COVID-19:

- Session occurs over the phone or via video (see Section E3)

- Questions added to packet:
 - “How has the COVID-19 pandemic impacted you and your family?”
 - “What did you think of the phone/video session today instead of an in-person visit?”
- Intervention materials dropped off using contactless procedures (see Section E3)

E10 Post-intervention

Two RAs will complete the post-intervention session (within 2 weeks of last session), which will last about 60 minutes. Caregivers will be compensated \$50 for their time and children will be given a parent-approved prize. At this visit, RAs will:

- Administer the following measures:
 - Caregivers will report on any changes in monthly family income, education level, or in the family structure.
 - Caregivers will report on the duration and number of times the child has been hospitalized due to asthma or visited the ED because of asthma in the last 12 months. This information will be verified by hospitalization and ED visit information from insurance companies and health systems.
 - Caregivers will report on the number of times their child missed school due to asthma in the last 12 months. This information will be verified by absentee data from the child’s school.
 - Caregivers will report on the child’s asthma medication name, dose, and refill information. We will also collect pharmacy refill data.
 - Caregivers and children will complete the Childhood Asthma Control Test (cACT) jointly, which measures the frequency of daytime and nighttime asthma symptoms, activity limitations, and perception of disease control.
 - Caregivers will report on number of symptom free days in the last 14 days on the Asthma Assessment Form.
 - Children will complete the Pediatric Asthma Quality of Life Questionnaire (PAQLQ).
 - Caregivers will complete the Pediatric Asthma Caregiver Quality of Life Questionnaire (PACQLQ) and report on their own quality of life.
 - Caregivers will complete the Asthma Self-Efficacy Management Questionnaire (ASMQ), Perceived Stress Scale (PSS), Centers for Epidemiologic Studies Depression Scale (CES-D), and Stressful Life Events and Conditions Checklist (SLECC).
- Complete a brief semi-structured interview with the parent and child. Questions will ascertain:
 - Family satisfaction with the intervention sessions
 - Whether they would recommend the program to a friend
 - Perceived usefulness of the interventions
 - What behavioral changes they made because of the program
 - Changes they have seen in their child’s daily asthma symptoms (if any)

Changes due to COVID-19:

- Session occurs over the phone or via video (see Section E3)
- Question added to packet
 - How has COVID-19 impacted your family?,” “How has COVID-19 impacted your child’s asthma care?,” “What has it been like not being able to access your child’s school nurse for asthma care?”
- Payment occurs via contactless payment drop-off (see Section E3) or via e-gift card.

E11 3-month follow-up

Two RAs will complete the 3-month follow-up session in the family’s home. Caregivers will be compensated \$70 for their time and children will be given a parent-approved prize. At this visit, RAs will:

- Administer the following measures:
 - Caregivers will report on the duration and number of times the child has been hospitalized due to asthma or visited the ED because of asthma since the post-intervention session. This information will be verified by hospitalization and ED visit information from insurance companies and health systems.

- Caregivers will report on the number of times their child missed school due to asthma in the last 3 months. This information will be verified by absentee data from the child's school.
- Caregivers will report on the child's asthma medication name, dose, and refill information. We will also collect pharmacy refill data.
- Caregivers and children will complete the Childhood Asthma Control Test (cACT) jointly, which measures the frequency of daytime and nighttime asthma symptoms, activity limitations, and perception of disease control.
- Caregivers will report on number of symptom free days in the last 14 days on the Asthma Assessment Form.
- Children will complete the Pediatric Asthma Quality of Life Questionnaire (PAQLQ).
- Caregivers will complete the Pediatric Asthma Caregiver Quality of Life Questionnaire (PACQLQ) and report on their own quality of life.
- Caregivers will complete the Asthma Self-Efficacy Management Questionnaire (ASMQ), Perceived Stress Scale (PSS), Centers for Epidemiologic Studies Depression Scale (CES-D), and Stressful Life Events and Conditions Checklist (SLECC).

Changes due to COVID-19:

- Session occurs over the phone or via video (see Section E3)
- Question added to packet
 - How has COVID-19 impacted your family?,” “How has COVID-19 impacted your child’s asthma care?,” “What has it been like not being able to access your child’s school nurse for asthma care?”
- Payment occurs via contactless payment drop-off (see Section E3) or via e-gift card.

E12 6-month follow-up

Two RAs will complete the 6-month follow-up session in the family's home. Caregivers will be compensated \$80 for their time and children will be given a parent-approved prize. At this visit, RAs will:

- Administer the following measures:
 - Caregivers will report on the duration and number of times the child has been hospitalized due to asthma or visited the ED because of asthma in the last 3 months. This information will be verified by hospitalization and ED visit information from insurance companies and health systems.
 - Caregivers will report on the number of times their child missed school due to asthma in the last 3 months. This information will be verified by absentee data from the child's school.
 - Caregivers will report on the child's asthma medication name, dose, and refill information. We will also collect pharmacy refill data.
 - Caregivers and children will complete the Childhood Asthma Control Test (cACT) jointly, which measures the frequency of daytime and nighttime asthma symptoms, activity limitations, and perception of disease control.
 - Caregivers will report on number of symptom free days in the last 14 days on the Asthma Assessment Form.
 - Children will complete the Pediatric Asthma Quality of Life Questionnaire (PAQLQ).
 - Caregivers will complete the Pediatric Asthma Caregiver Quality of Life Questionnaire (PACQLQ) and report on their own quality of life.
 - Caregivers will complete the Asthma Self-Efficacy Management Questionnaire (ASMQ), Perceived Stress Scale (PSS), Centers for Epidemiologic Studies Depression Scale (CES-D), and Stressful Life Events and Conditions Checklist (SLECC).

Changes due to COVID-19:

- Session occurs over the phone or via video (see Section E3)
- Question added to packet
 - How has COVID-19 impacted your family?,” “How has COVID-19 impacted your child’s asthma care?,” “What has it been like not being able to access your child’s school nurse for asthma care?”
- Payment occurs via contactless payment drop-off (see Section E3) or via e-gift card.

E13 9-month follow-up

Two RAs will complete the 9-month follow-up session in the family's home. Caregivers will be compensated \$100 for their time and children will be given a parent-approved prize. At this visit, RAs will:

- Administer the following measures:
 - Caregivers will report on the duration and number of times the child has been hospitalized due to asthma or visited the ED because of asthma in the last 6 months. This information will be verified by hospitalization and ED visit information from insurance companies and health systems.
 - Caregivers will report on the number of times their child missed school due to asthma in the last 6 months. This information will be verified by absentee data from the child's school.
 - Caregivers will report on the child's asthma medication name, dose, and refill information. We will also collect pharmacy refill data.
 - Caregivers and children will complete the Childhood Asthma Control Test (cACT) jointly, which measures the frequency of daytime and nighttime asthma symptoms, activity limitations, and perception of disease control.
 - Caregivers will report on number of symptom free days in the last 14 days on the Asthma Assessment Form.
 - Children will complete the Pediatric Asthma Quality of Life Questionnaire (PAQLQ).
 - Caregivers will complete the Pediatric Asthma Caregiver Quality of Life Questionnaire (PACQLQ) and report on their own quality of life.
 - Caregivers will complete the Asthma Self-Efficacy Management Questionnaire (ASMQ), Perceived Stress Scale (PSS), Centers for Epidemiologic Studies Depression Scale (CES-D), and Stressful Life Events and Conditions Checklist (SLECC).

Changes due to COVID-19:

- Session occurs over the phone or via video (see Section E3)
- Question added to packet
 - How has COVID-19 impacted your family?,” “How has COVID-19 impacted your child’s asthma care?,” “What has it been like not being able to access your child’s school nurse for asthma care?”
- Payment occurs via contactless payment drop-off (see Section E3) or via e-gift card.

E14 Metrics from CHWs, Healthy Homes, and PCPs

Program-specific data will be gathered from CHWs, Healthy Homes, school nurses, and child medical homes. All metrics will be entered directly into REDCap. This information will be used to assess the implementation of the project, including whether short-term outcomes were achieved.

Metrics from home visits. CHWs and Healthy Homes assessors will complete electronic productivity reports regarding their productivity on the study as staff, including time spent on each component of the session, content that was covered, and content that was not (and reason). Information on family questions and barriers described will also be entered in reports. CHWs will also be prompted to ask caregivers a series of paper questionnaires at each visit related to symptoms, asthma control, medication use and changes, healthcare utilization, and missed school days. In their productivity reports, Healthy Homes will note observations of the home environment, as well as document education shared, materials provided to the family, and referrals to MLP-R. Visual observations about the home environment include exterior and interior observations that pertain to the Asthma Environment Checklist from EPA (e.g., standing water, presence of tobacco smoke, mold, pests, or pets).

Metrics from nurses. Nurses will record data on paper forms or in an electronic file if preferred related to interactions with student, any reported health care utilization from student, school absences (for CHW follow-up), and care coordination activity (with family and/or PCP).

Metrics from health systems. Information from health systems (area hospitals) will contain patient identifying information. Data will include information related to units, duration, and frequency of ED visits and hospitalizations due to asthma in the last year.

Metrics from medical homes. CHWs and the project coordinator will document children's visits to their primary care provider or other physician for asthma care. CHWs will ask caregivers to report on any child asthma-related visits to a provider throughout their time in the study; number of visits and reason for visit will be recorded, including whether it was a preventative or an urgent visit. If the child is enrolled in the school intervention group, CHWs or the project coordinator will communicate with the provider's office to ensure that the school has an asthma action plan and medication release form on file at the school.

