2.d.i. Changes to recruitment and consent process due to COVID-19: Recruitment in the community will be limited to remote options (e.g., as a part of virtual newsletters or emailed flyers). School nurses will still call potentially eligible families, we will still receive lists of children seen at VCU and BSHS, and letters will be mailed from provider offices. Families will be screened using our IRB approved screening materials. If a family screens eligible, the caregiver will be told that, "Due to COVID-19 and recommendations from the Health Department, and for the safety of families and our staff, we are now conducting RVA Breathes remotely. This means that the consent process and all research and intervention sessions will be conducted over the phone or video." A phone or video session will then be scheduled to conduct the verbal consent process and complete baseline measures. Questions will be asked to the parent and then to the child separately. If the child is not available or is not comfortable answering questions, these will be marked as missing data. IRB has approved a waiver of documentation of consent for parents in RVA Breathes. This is for their participation in the study and for the participation of their child. We will instead obtain verbal consent and will document in our research record using a consent documentation form that records that consent was given, what day/time it was given, and who was present for the discussion. We are also approved to waive child assent, which is recorded on the consent documentation form.

2.e Randomization Method and Blinding

Families will be randomized at the school level. In consultation with RPS, we will match elementary schools based on demographics and location, and whether school nurses travel among schools; 8-9 schools will be included in each condition. We will use a block randomization scheme. After the baseline session is complete, the project coordinator will randomize the family to one of the 3 conditions based on the child's school. Given the nature of our program, it will not be possible to blind participants or study staff to their condition. Analysts collecting data from insurance companies will be blind to condition.

2.f Risks and Benefits

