Contact information for potentially eligible participants will be given to study RAs and the project coordinator. Families will then be contacted by study staff to determine eligibility and interest. During their initial contact, potential participants will complete a screening questionnaire (which confirms their family's eligibility). Caregivers will be asked to provide their verbal consent prior to beginning the screening interview. This over the phone screening questionnaire will include questions regarding child age, school, parent/caregiver and child relationship, and questions regarding the child's asthma diagnosis. If the caregiver and child are eligible and interested, a baseline visit will be scheduled within two weeks of the screening phone call.

E2 Schedule of Measurements

This table includes all measure content, including in which visit they are collected. Exact measure names are presented in the description of sessions.

Forms	Content	Administered by	When/How Often
Potential Participant Information	Contact information for potential participants (includes caregivers and children who are and are not selected to participate)	Project coordinator	Pre-enrollment
Eligibility and Enrollment	Inclusion and exclusion criteria for the study; Assignment into intervention arms and wave; IRB consent/assent	Project coordinator	Pre-enrollment
Caregiver Release	Signature of caregiver authorizing study personnel to contact the child's school nurses, PCP and/or asthma provider	Research assistants (RA)	Baseline session
Demographic Information	Caregiver and child race, ethnicity, gender	RA	Baseline session

Psychosocial Characteristics	Caregiver and child characteristics on social determinants of health, stress, and depressive symptoms	RA or CHW	Baseline, post intervention, 3-month, 6-month, and 9-month follow up sessions
Health Care Utilization	Inpatient and emergency department utilization	RA or CHW	
Medication Usage	Prescription medication history and refills	RA or CHW	
Asthma Symptoms and Control	Asthma control, symptoms, quality of life, self-management skills	RA or CHW	
School Nurse Log	School attendance, visit to nurse, medication given at school	RN or RA	
Month 1 Session – CHW	Documenting info on asthma basics	CHW	Month 1 Session
Month 1 Session – HH	Comprehensive home environment assessment	HH	
Month 4 Session – CHW	Documenting info on increasing self-management	CHW	Month 4 Session

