- To baseline/follow-up session questionnaires: “How has COVID-19 impacted your family?,” “How has COVID-19 impacted your child’s asthma care?,” “What has it been like not being able to access your child’s school nurse for asthma care?”

Change in school nurse intervention due to COVID-19: Per RPS protocol, school nurses will be contacting all students with a health condition at least once over the phone during the fall semester. This will include RVA Breathes participants. When a school nurse speaks with an RVA Breathes family, the school nurse will complete a modified data form that has been adapted for a non-clinic setting. This interaction could happen at any time throughout 2020.

E4 Baseline Session

Two RAs will attend the baseline session, which will last about 90 minutes. Caregivers will be compensated \$30 for their time and children will be given a parent-approved prize. At this visit, RAs will:

- Obtain and document consent from subject on study consent form, as well as child assent. This includes parental consent for their own participation and their child's participation.
- Verify inclusion/exclusion criteria.
- Administer the following measures:
 - Caregivers will report on family demographic information including caregiver and child's race/ethnicity, age, sex, monthly family income, education level, information on family structure, and their relationship to child.
 - Caregivers will report on the duration and number of times the child has been hospitalized due to asthma or visited the ED because of asthma in the last 12 months. This information will be verified by hospitalization and ED visit information from insurance companies and health systems.
 - Caregivers will report on the number of times their child missed school due to asthma in the last 12 months. This information will be verified by absentee data from the child's school.
 - Caregivers will report on the child's asthma medication name, dose, and refill information. We will also collect pharmacy refill data.
 - Caregivers and children will complete the Childhood Asthma Control Test (cACT) jointly, which measures the frequency of daytime and nighttime asthma symptoms, activity limitations, and perception of disease control.
 - Caregivers will report on number of symptom free days in the last 14 days on the Asthma Assessment Form.
 - Children will complete the Pediatric Asthma Quality of Life Questionnaire (PAQLQ).

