Missingness. We will handle missing data in several ways. Health utilization is being reported by caregivers (self-report) and we are also receiving health encounter data from insurers and hospital billing systems. For families that have been lost to follow-up but have not asked to withdraw from the study, we will still receive and use their objective health encounter data. This will limit missingness related to our main outcomes when using encounter data. For self-report data, we will conduct a sensitivity analysis on raw data and examine patterns of missingness. We then will use a pattern-mixture model with multiple imputation from other available timepoints. We can then compare those analyses to analyses using objective health encounter data.

Missing Data and Participant Attrition Strategies:

The primary analysis will follow the approved statistical analysis plan, without any changes for missing data. After fitting this model, missing data patterns will be examined and their patterns will be examined, in particular looking for a monotone missing data pattern indicative of attrition. If, as expected, we find that there is a monotone pattern of missing data (i.e., once an individual misses an observation, they will be missing all subsequent observations), this will provide evidence that the missing completely at random (MCAR) and missing at random (MAR) assumptions may be violated. To examine the impact of monotone missing data, multiple imputation using a pattern-mixture model with control-based imputation will be utilized. We will create 50 imputed datasets for the outcomes and analyze them using the primary analysis model. The results from these 50 analyses will then be combined to derive an overall result. This will allow us to perform a sensitivity analysis to see how much bias the missing data causes.

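### Masking is stated only for insurer-data analysts; it should extend to hospital encounter data and, as far as possible, to the RAs who assess outcomes, and E2 should not let CHWs collect them

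*Protocol*

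**What the plan says.** Protocol section 2.e (Randomization Method and Blinding) states: "Given the nature of our program, it will not be possible to blind participants or study staff to their condition". It then makes one exception: "Analysts collecting data from insurance companies will be blind to condition". Allocation follows the school and comes after baseline: "the project coordinator will randomize the family to one of the 3 conditions based on the child's school".

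Outcome collection is described in two places. E4 says "Two RAs will attend the baseline session, which will last about 90 minutes", and E10 to E13 likewise give the post-intervention and 3-, 6- and 9-month sessions to two RAs. The E2 table instead lists either an RA or a CHW for the utilization, medication, symptom/control/quality-of-life and psychosocial forms.

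The encounter data for the primary composite come from more than one source. The SAP (Missingness) says "we are also receiving health encounter data from insurers and hospital billing systems". E14 of the protocol adds: "Information from health systems (area hospitals) will contain patient identifying information". Neither document says who handles the hospital data or whether that person knows the condition.

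Two further entries bear on the point. At post-intervention (E10) the RAs are to "Complete a brief semi-structured interview with the parent and child", with questions about the intervention sessions. The E2 eligibility and enrollment form, completed before enrollment by the project coordinator, includes "Assignment into intervention arms and wave".

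**The concern.** Section 2.e gives one reason for leaving all study staff unblinded: the nature of the program. That holds for the people who deliver it, but it does not by itself explain why outcome assessors or record handlers must know the arm.

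Two things are at stake. The first is the Aim 2 measures (asthma control, symptoms, quality of life). The SAP states the expected direction in advance, with the intervention groups superior, and the measures are taken in interviews, by phone or video after March 2020. A difference in how questions are put or answers recorded would enter the Group by Time term. The second is the primary composite, which counts asthma-related inpatient and ED visits. If anyone on the study side judges which hospital encounters count, that judgment should be made without knowledge of the arm, as is already arranged for insurer data.

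**Working it through.** **Role by role, from the documents**

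| Role | Delivers intervention? | Collects or handles outcomes? | Masking stated? |
|---|---|---|---|
| CHWs | Yes (E5, E7-E9) | Possibly (E2: RA or CHW); also ask about symptoms, control and utilization at intervention visits (E14) | No; cannot be masked |
| Healthy Homes assessors | Yes (E5, E7-E9) | Home environment only (E14) | No; cannot be masked |
| School nurses | Yes, in the school arm (E5, E7-E9) | School log (E2) | No; cannot be masked |
| RAs | No task described | Baseline and four later sessions (E4, E10-E13) | No; covered by the blanket statement |
| Insurer-data analysts | No | Primary composite, insurer source | Yes (2.e) |
| Hospital-data handlers | Not described | Primary composite, hospital source | Not stated |

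Three points follow. The stated reason for no blinding does not reach the RAs. One primary outcome has two encounter sources, and masking is stated for only one of them. E2 conflicts with E4 and E10-E13 on who administers the measures.

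E2 and 2.e also conflict on timing: E2 puts arm assignment on a pre-enrollment form, while 2.e assigns after baseline.

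**How much could it matter?** The plan gives no figure for assessor or classification bias, so there is nothing to reproduce. Both calculations below are illustrations on assumed inputs.

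*Interview measures (Gaussian).* Inputs: 80 per arm (240/3, from the SAP sample size). Assumed: pre-post correlation 0.5, no true effect, and a shift d due entirely to the interviewer.

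- SE of the difference in change = √(2(1 − 0.5)) × √(2/80) = 0.158 SD.
- P(reject) = Φ(−z + d/SE) + Φ(−z − d/SE).
- School clustering, with 10 children per school (SAP) and an assumed ICC, multiplies the SE by √(1 + 9 × ICC). This gives 0.165 at ICC 0.01 and 0.190 at ICC 0.05.

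| Shift d | α = .05, ICC 0 | α = .05, ICC 0.05 | α = .0167, ICC 0 | α = .0167, ICC 0.05 |
|---|---|---|---|---|
| 0.1 SD | 10% | 8% | 4% | 3% |
| 0.2 SD | 24% | 18% | 13% | 9% |
| 0.3 SD | 47% | 35% | 31% | 21% |

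With ICC 0 and d = 0.2, moving the correlation from 0.3 to 0.7 gives 19% to 37% at .05.

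*Primary count.* Inputs from the SAP: 8 schools per arm (24/3), 10 children each, α = .0167, and a 9-month rate of 1.68 × 0.65 = 1.09 in both arms (control baseline rate less a 35% reduction). The between-school coefficient of variation (CV) ranges from 0.0502 to 0.1820. Assumed: no true effect, a comparison of post-period rates only, and visits in one arm under-counted by a fraction u.

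- Variance of the log rate in an arm = (1/8) × (1/(10 × rate) + CV²). The two arms' variances are added, and the rate in the affected arm is 1.09 × (1 − u).
- Example, u = 0.20 and CV = 0.0502: SE = 0.162 and |log 0.8| = 0.223, so P(reject) is about 15%.
- Over the CV range, P(reject) is 2.1-2.3% for u = 5%, 3.7-4.3% for u = 10% and 12-15% for u = 20%, against a nominal 1.67%.

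**The case against.** The strongest reply is that masking RAs would achieve little. Caregivers and children know their arm and report on themselves, so respondent bias remains whoever asks the questions. Arm follows school, with an average of 10 enrolled children in each of 24 schools, and school is asked at screening (E1), so one family's disclosure can unmask a whole school. Follow-ups were planned in the home, where supplied items such as air purifiers (E3) may be visible. All of this stands. It limits what masking can do, but it does not justify leaving the separate interviewer contribution uncontrolled.

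Timing also counts. Section B3 places 217 families under procedures before March 13, 2020, and the SAP is dated June 2022. Sessions already held cannot be changed.

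Three stronger readings are tempting, and the documents do not support them:

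- *Hospital-data handlers are unblinded.* The documents are silent. Identifiable records are not arm information, and no section describes study staff deciding which encounters are asthma-related. Masking is not stated; nothing more can be said.
- *The enrollment form shows RAs the arm.* E2 gives that form to the project coordinator, who also randomizes. Nothing shows it reaching RAs. The timing mismatch is a separate inconsistency.
- *Bias in the primary outcome could not be told apart from an effect.* Caregiver-reported utilization is verified against insurer and health-system data (E4, E10-E13), and the SAP plans to compare self-report analyses with encounter data. Absences are checked against school records and refill data are collected. The argument keeps its force mainly for Aim 2.

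**Conclusion.** The point holds as a gap in stated masking and an inconsistency about who collects outcomes. Masking is stated for one of two encounter sources feeding the same composite. RAs are left unblinded for a reason that does not apply to their role. E2 permits CHWs, who deliver the intervention, to administer outcome forms. The exposure is mainly in the Aim 2 interview measures and smaller for utilization.

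The size of any bias is unknown. The 0.1-0.3 SD shifts, the correlations, the ICCs and the under-counting fractions are assumptions with no basis in the documents. The calculations show only that modest differential ascertainment would matter at this sample size. Changing the plan is worthwhile because most of the remedy is cheap, and masking the record work has no real downside.

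**What to change.** 1. Amend 2.e so that staff who extract or classify encounters, from insurers or hospitals, are blind to condition. Limit the statement that blinding is impossible to participants and those who deliver the intervention.
2. Amend E2 so that RAs, not CHWs, administer baseline and follow-up measures, in line with E4 and E10-E13.
3. Withhold the school-to-arm list and the arm field from RAs as far as possible, and hold the post-intervention satisfaction interview after all measures are complete.
4. Reconcile E2's pre-enrollment arm assignment with the post-baseline assignment in 2.e.
5. For sessions already held, report the actual blinding status of each role.

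The cost is protocol wording, data-access rights and session order. RA masking will be incomplete: arm follows school, families may disclose visits, items may be seen in the home, and the satisfaction interview reveals the arm before the three later follow-ups. Keeping the interviewing RA away from that family's later visits would close the last route, but each visit uses two RAs and this may need extra staff, so it is not requested.
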